12.4.1.1 Baseline Comparability

Not applicable.

Confidentiality Statement

Data and information contained in this document are considered to constitute trade secrets and confidential commercial information, and the legal protections provided to such trade secrets and confidential information are hereby claimed under the provisions of applicable law. No part of this document may be publicly disclosed without the written consent of Philip Morris Products S.A.

12.4.1.2 Descriptive Analysis

Endpoints will be summarized using the randomized and the PK population.

12.4.1.3 Missing Data Strategy

See Section [12.1.3](#) for missing data strategy.

12.4.1.4 Main Analysis

A mixed model analysis of variance (ANOVA) will be conducted on AUC_{0-24h} , C_{max} , and AUC_{0-t} endpoints in the natural logarithmic scale.

The model will include terms for sequence, period, product exposure as fixed effects and subject as a categorical random effect modeling the within subject correlations. The ANOVA analysis could be performed using the following SAS code:

```
PROC MIXED data=<> method=REML;
class subject sequence period product;
model log(parameter) = sequence period product/ddfm=KR;
repeated product / subject=subject type=csh;
lsmeans product / pdiff=control("CIG") cl alpha=0.05;
RUN;
```

The results of this analysis for each of are presented in terms of geometric least square ratios and 95% confidence intervals for the THS / CIG ratio.

This approach is consistent with the guidelines in the European Medicines Agency's guidelines for bioequivalence investigations [\[24\]](#) and FDA's Center for Drug Evaluation and Research [\[25\]](#).

The analysis of T_{max} will be performed by conducting a Wilcoxon signed rank test and calculating the median T_{max} for each product along with the Hodges-Lehmann [\[26\]](#) estimate of the median difference between products, and the related 95% CI. This analysis could be performed using the following SAS code:

```
PROC NPAR1WAY hl(refclass=<>) alpha=.05 data=<> hl;
class TRT;
var AVAL;
ods output HodgesLehmann=HodgesLehmann;
RUN;
```

12.4.1.5 Sensitivity Analyses

In case of any uncorrected nicotine concentration at T_0 [μC_0] greater than 5% of their uncorrected maximum value, a sensitivity analysis of the PK endpoints will be performed similarly to the main analysis, whereby data of these subjects for this specific study day will be excluded from the analysis.

Confidentiality Statement

Data and information contained in this document are considered to constitute trade secrets and confidential commercial information, and the legal protections provided to such trade secrets and confidential information are hereby claimed under the provisions of applicable law. No part of this document may be publicly disclosed without the written consent of Philip Morris Products S.A.

12.4.1.6 Supplementary Analysis

No supplementary analysis is foreseen.

12.5 Secondary Objectives

12.5.1 Secondary Objective 1

To evaluate pharmacodynamic (PD) effects (subjective effects) of a single use of a THS with either a regular or a menthol stick or of a single CIG. Endpoints will be analysed by investigational product (IP).

Descriptive statistics (n, mean, SD, CV%, SEM, minimum, Q1, median, Q3, maximum, and 95% CI of mean) VAS *Craving* assessment, VAS *Liking* assessment, and VAS *Intention to Use Again* assessment will be provided by IP and assessment time point, when applicable. Change from baseline (pre-product use) for VAS *Craving* score will be summarized by study product and assessment time point. Individual responses will be listed. Summaries will be further stratified by sex.

12.5.2 Secondary Objective 2

This analysis refers to the secondary objective 2 defined in Section 3.2, which is to evaluate the safety of test products during the study.

In general, all safety data will be listed and tabulated. Safety variables collected during exposure periods will also be reported by randomization sequence.

AE data will serve for the assessment of safety. Other safety variables monitored in this study will include the incidence of THS product events including malfunction/misuse; vital signs (systolic and diastolic blood pressure, pulse rate, respiratory rate); spirometry; ECG data; clinical chemistry, hematology, and urine analysis safety panel; physical examination; concomitant medication.

The number and percentage of subjects with AEs, SAEs, and IP events will be tabulated by system organ class and preferred term. Summaries will also be presented for AEs leading to discontinuation, AEs leading to death, AEs by relatedness to product exposure, AEs by severity, and laboratory AEs. Tabulations will be performed for both the number of subjects experiencing an event and the number of events.

Safety laboratory assessments are performed on Day -1 and Day 3 in the morning prior to product use (Appendix A). Any lab related AEs on Day 3 will be assigned to the product used on the previous day.

Summary tables showing actual values and change from baseline of clinical findings will be provided for spirometry, ECGs, vital signs, and laboratory parameter. Descriptive statistics will be summarized by study day for ECG, vital signs and for laboratory parameters.

Confidentiality Statement

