7.5 Laboratory Assessments

7.5.1 Clinical Chemistry, Hematology, and Urine Analysis for Safety Panel

Hematology and clinical chemistry analysis will be assessed as per Schedule of Events. Subjects should have fasted for at least 6 hours prior to safety laboratory assessments, except at Discharge and Early termination where non-fasting samples can be used. Tests will be conducted at a local laboratory ([Appendix B](#)). If during the Screening visit a blood sample is not suitable for analysis (e.g., blood clotting) a re-test should be performed for the specific parameters which are not available. Safety urine analysis will be assessed at Screening, Baseline and at Discharge or at Early termination.

Parameters to be tested are listed in [Table 1](#).

Confidentiality Statement

Data and information contained in this document are considered to constitute trade secrets and confidential commercial information, and the legal protections provided to such trade secrets and confidential information are hereby claimed under the provisions of applicable law. No part of this document may be publicly disclosed without the written consent of Philip Morris Products S.A.

Table 1 Clinical Laboratory Parameters for Safety Panel

| Hematology | Clinical Chemistry | Urine analysis |
|--|---|---|
| 
 • Hematocrit • Hemoglobin • Mean corpuscular hemoglobin • Mean corpuscular hemoglobin concentration • Mean corpuscular volume • Platelet count • Red blood cell count • White blood cell count • Differential* WBC count: 
 - Neutrophils - Basophils - Eosinophils - Lymphocytes - Monocytes | 
 • Albumin • Total protein • Alkaline phosphatase • Alanine aminotransferase • Aspartate aminotransferase • Blood urea nitrogen • Creatinine • Gamma-glutamyl transferase • Glucose • Lactate dehydrogenase • Potassium • Sodium • Total bilirubin • Direct bilirubin • Total cholesterol • Triglycerides | 
 • pH • Bilirubin • Glucose • Nitrite • Red blood cell traces • Protein • Specific gravity |

*Differential WBC count both percentage and absolute

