Appendix A Schedule of Events

Study Assessments

| | Screening | Baseline | Exposure | | | Safety Follow-up |
|--|-------------------|----------|----------|-------|-------------------|------------------|
| Visit | 1 | 2 | | | Early Termination | Phone contact |
| Study Day (D) | Day -28 to Day -2 | Day -1 | Day 1 | Day 2 | Day 3 | + 3 Days |
| Informed consent | • | | | | | |
| FTND | • | | | | | |
| Information on risks of smoking, smoking cessation advice, and briefing on THS | • | • | | | • | • |
| TNP use history questionnaire | • | • | | | | |
| Inclusion/exclusion criteria | • | • | | | | |
| ECG | • | • | | | • | • |
| Spirometry | • | • | | | • | • |
| Demographics | • | | | | | |
| Medical history | • | | | | | |
| Concomitant diseases and medication | • | • | • | • | • | • |
| Physical examination | • | | | | | |
| Body height, body weight, BMI | • | | | | | |
| Vital signs | • | • | • | • | • | • |
| B: HIV, HBV, and HCV | • | | | | | |
| Identification of CIG brand | • | | | | | |

Confidentiality Statement

Data and information contained in this document are considered to constitute trade secrets and confidential commercial information, and the legal protections provided to such trade secrets and confidential information are hereby claimed under the provisions of applicable law. No part of this document may be publicly disclosed without the written consent of Philip Morris Products S.A.

| Visit | Screening | Baseline | Exposure | | | Safety Follow-up |
|---|-------------------|----------|----------|-------|-------------------|------------------|
| | 1 | 2 | | | Early Termination | Phone contact |
| Study Day (D) | Day -28 to Day -2 | Day -1 | Day 1 | Day 2 | Day 3 | + 3 Days |
| U: Drug screen | • | • | | | | |
| U: Cotinine test | • | • | | | | |
| U: Pregnancy test | • | • | | | • | • |
| Alcohol breath test | • | • | | | | |
| B & U: Safety laboratory panel (non-fasting Day 3 + ET) | • | • | | | • | • |
| THS demonstration (without use) | • | | | | | |
| Randomization | | • | | | | |
| IP use (THS or CIG) | | | • | • | • | |
| B: plasma nicotine samples | | | • | • | • | |
| VAS Craving assessment | | | • | • | • | |
| VAS Liking assessment | | | • | • | • | |
| VAS Intention to Use Again assessment | | | • | • | • | |
| AE/SAE recording | • | • | • | • | • | • |
| Product events, malfunctions, misuse | | | • | • | • | • |
| Phone call at end of SFU period | | | | | | • |

Abbreviations:

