## 8.9 Clinical Laboratory Tests (Serum Chemistry, Hematology, and Urinalysis)

Clinical laboratory evaluations (clinical chemistry, hematology, and urinalysis) will be performed at Screening, Admission (Day -1), and at the time of discharge (Day 3) or as early termination assessments, as applicable.

Out-of-normal range flags will be recorded as follows: high (H) and low (L) for numerical results and did-not-match (\*) for categorical results. If a value fails the reference range, it will automatically be compared to a computer clinically significant (CS) range. If the value falls within the computer CS range, it will be noted as "N" for not clinically significant. If the value fails (i.e., fall outside of the CS range) the computer CS range, it will be flagged with a

Philip Morris Products S.A.  
THS Induction device and regular or menthol sticks, P1-PK-12  
[REDACTED] CA39924

---

"Y" which prompts the PI to determine how the out-of-range value should be followed using 4 Investigator flags: "N", not clinically significant, "R", requesting a recheck, "^", checking at the next scheduled visit, or "Y", clinically significant. To distinguish the PI flag from the computer CS range flags, the PI flags of "N" and "Y" will be presented as "-" and "+", respectively, in the data listing. Additionally, a derived flag based on a search of the PI comments for a comment of "CS" or "Clinically Significant" will be used. The derived flag will be populated with "+" if the positive clinically significant determination is found in the comments for cases when the PI flag is populated with a "^" or a "R".

Out-of-range values and corresponding recheck results will be listed. CTCAE laboratory grading (version 5.0) will be included as well. Other lab results within this panel and time point will also be listed for this subject. Results that are indicated as CS by the PI will be listed in the table.

For all numeric laboratory values, descriptive statistics will be presented for each laboratory test by time point (baseline and discharge). Change from baseline will be summarized in a similar manner. Baseline is defined as the result closest and prior to the first product administration, which may include unscheduled or recheck results. This will typically be the result collected on Admission (Day -1). Post product use unscheduled events or rechecks will not be included in summaries. Similarly, early termination results will not be included in summaries.

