H = Above reference range

Computer: Y = Clinically significant

PI Interpretation: R = Recheck requested, + = Clinically significant

If no event meet this criteria then include a statement as follows:

"There were no clinical laboratory results documented as clinically significant by the PI."

Philip Morris Products S.A.

THS Induction device and regular or menthol sticks, P1-PK-12

CA39924

Page 1 of X

Table CLBD Clinical Laboratory Summary and Change From Baseline - <Clinical Laboratory Panel> (Safety Population)

Laboratory Test (units)	Reference Range	Time Point	Statistic	Randomized Product Sequence					
				XXX (N = X)	XXX (N = X)	XXX (N = X)	XXX (N = X)	XXX (N = X)	XXX (N = X)
Testname (unit)	< - >#	Baseline	n	X	X	X	X	X	X
			Mean	X.X*	X.X	X.X	X.X	X.X	X.X*
			SD	X.XX	X.XX	X.XX	X.XX	X.XX	X.XX
			Minimum	XX	XX	XX	XX	XX	XX
			Median	X.X	X.X	X.X	X.X	X.X	X.X
			Maximum	XX	XX	XX	XX	XX	XX
		Discharge	Absolute	n	X	X	X	X	X
			Mean	X.X^	X.X	X.X	X.X^	X.X	X.X
			SD	X.XX	X.XX	X.XX	X.XX	X.XX	X.XX
			Minimum	XX	XX	XX	XX	XX	XX
			Median	X.X	X.X	X.X	X.X	X.X	X.X
			Maximum	XX	XX	XX	XX	XX	XX
		Change	n	X	X	X	X	X	X
			Mean	X.X^	X.X	X.X	X.X^	X.X	X.X
			SD	X.XX	X.XX	X.XX	X.XX	X.XX	X.XX
			Minimum	XX	XX	XX	XX	XX	XX
			Median	X.X	X.X	X.X	X.X	X.X	X.X
			Maximum	XX	XX	XX	XX	XX	XX

Programmer Note: Means at specific time points will be flagged (with a \*) if they are above or below the reference range. This only applies to the clinical laboratory results (i.e., not the change from baseline or any other endpoints). Time Point column will match those found in Section 8.9 of the SAP.

P1R: < >

P1M: < >

CIG: < >

Baseline is the last measurement collected prior to the first product administration.

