# = Lowest of the lower ranges and highest of the higher ranges are used. Refer to Appendix 16.1.10.1 for the breakdown.

\* = Above reference range; ^ = Below reference range

Program: /CAXXXX/sas\_prg/stsas/tab/programname2022Q1.sas DDMMYYYY HH:MM

Philip Morris Products S.A.

THS Induction device and regular or menthol sticks, P1-PK-12

CA39924

Page 1 of X

Table CLBS Clinical Laboratory Shift From Baseline - Serum Chemistry (Safety Population)

Laboratory Test (units)	Randomized Product Sequence	Time Point	Baseline L			Baseline N			Baseline H		
			Post Use			Post Use			Post Use		
			L	N	H	L	N	H	L	N	H
Testname (unit)	XXX	Discharge	X	XX	X	X	XX	X	X	XX	X
	XXX	Discharge	X	XX	X	X	XX	X	X	XX	X
	XXX	Discharge	X	XX	X	X	XX	X	X	XX	X
	XXX	Discharge	X	XX	X	X	XX	X	X	XX	X
	XXX	Discharge	X	XX	X	X	XX	X	X	XX	X
	XXX	Discharge	X	XX	X	X	XX	X	X	XX	X

Programmer Note: For urinalysis, the following footnote is used since the categories of N and O will be used instead of L, N, H:  
 N = Within reference range; O = Outside reference range

P1R: < >

P1M: < >

CIG: < >

Baseline is the last measurement collected prior to the first product administration.

N = Within reference range; L = Below reference range; H = Above reference range

Program: /CAXXXX/sas\_prg/stsas/tab/programname2022Q1.sas DDMMYYYY HH:MM

Philip Morris Products S.A.

THS Induction device and regular or menthol sticks, P1-PK-12

CA39924

Page 1 of X

Table CVS Vital Sign Summary and Change From Baseline (Safety Population)

Vital Sign (units)	Time Point	Statistic	Randomized Product Sequence					
			XXX (N = X)	XXX (N = X)	XXX (N = X)	XXX (N = X)	XXX (N = X)	XXX (N = X)
Testname (unit)	Baseline	n	X	X	X	X	X	X
		Mean	X.X	X.X	X.X	X.X	X.X	X.X
		SD	X.XX	X.XX	X.XX	X.XX	X.XX	X.XX
		Minimum	XX	XX	XX	XX	XX	XX
		Median	X.X	X.X	X.X	X.X	X.X	X.X
		Maximum	XX	XX	XX	XX	XX	XX
Day 2	Absolute	n	X	X	X	X	X	X
		Mean	X.X	X.X	X.X	X.X	X.X	X.X
		SD	X.XX	X.XX	X.XX	X.XX	X.XX	X.XX
		Minimum	XX	XX	XX	XX	XX	XX
		Median	X.X	X.X	X.X	X.X	X.X	X.X
		Maximum	XX	XX	XX	XX	XX	XX
Change	Change	n	X	X	X	X	X	X
		Mean	X.X	X.X	X.X	X.X	X.X	X.X
		SD	X.XX	X.XX	X.XX	X.XX	X.XX	X.XX
		Minimum	XX	XX	XX	XX	XX	XX
		Median	X.X	X.X	X.X	X.X	X.X	X.X
		Maximum	XX	XX	XX	XX	XX	XX

P1R: < >

P1M: < >

CIG: < >

Baseline is the last measurement collected prior to the first product administration.

Program: /CAXXXX/sas\_prg/stsas/tab/programname2022Q1.sas DDMMYYYY HH:MM

Philip Morris Products S.A.

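### Protocol 12.5.2 assigns Day 3 laboratory AEs to the Day 2 product on a pre-use draw that Appendix A does not state and that SAP 8.9 places at discharge

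*Protocol*

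**What the plan says.** Protocol 12.5.2 gives the premise, "Safety laboratory assessments are performed on Day -1 and Day 3 in the morning prior to product use", with a reference to Appendix A. The rule follows: "Any lab related AEs on Day 3 will be assigned to the product used on the previous day".

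The Appendix A row reads "B & U: Safety laboratory panel (non-fasting Day 3 + ET" and marks Day 3. It does not mention T0. Protocol 7.5.1 requires a 6-hour fast for safety samples, "except at Discharge and Early termination where non-fasting samples can be used".

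SAP 8.9 schedules the panel at Screening, at Admission "and at the time of discharge (Day 3) or as early termination assessments, as applicable". It adds that "descriptive statistics will be presented for each laboratory test by time point (baseline and discharge". A programmer note on the laboratory summary shell CLBD (SAP 12.3) says "Time Point column will match those found in Section 8.9 of the SAP". The laboratory shift shell, titled "Clinical Laboratory Shift From Baseline - Serum Chemistry (Safety Population", shows Discharge in every row under a post-use heading.

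For AEs in general, SAP 8.8 attributes an event arising in the washout between products to the product most recently used. It has no rule specific to laboratory AEs. It promises a summary of them, but none of the six tables listed under 14.3.1 is for laboratory AEs, so no shell note settles attribution. SAP 9 records no departure from the protocol.

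**The concern.** The previous-day rule is sensible only if its premise is true. When blood is drawn before the Day 3 product is used, the Day 2 product is the latest exposure. When blood is drawn at discharge, the Day 3 product is the latest, and a fixed previous-day rule skips it. The protocol states the premise once and supports it with a reference that does not contain it. The SAP and another protocol section point the other way.

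The safety of the test products is secondary objective 2, and AEs are tabulated by product. Day 3 is the only scheduled laboratory assessment after exposure, so no other visit can settle which product an abnormal value is counted under. A programmer following the protocol and one following SAP 8.8 could file the same laboratory AE under different products, and each could point to SAP 9 for support.

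**Working it through.** **1. How many Day 3 draws are there?** Protocol 7.6.2 gives about 60 mL for safety laboratory samples (80 mL for alternate subjects) at 20 mL per assessment.

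- 60 / 20 = 3 draws: Screening, Day -1, Day 3.
- 80 / 20 = 4 draws for alternates, who repeat Day -1.
- Check against the stated total: nicotine samples (14 + 13 + 11) × 5 mL = 190 mL, and 190 + 5 + 80 = 275 mL, as the protocol states.

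The budget therefore holds one Day 3 safety draw. It does not show when that draw is made, but a single draw cannot be both before use and at discharge.

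**2. When is it drawn?**

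| Place | Day 3 safety draw | Timing implied |
|---|---|---|
| Protocol 12.5.2 | Morning, before use | Pre-use |
| Appendix A (cited by 12.5.2) | Day 3 marked, fasting not required | None |
| Protocol 7.5.1 | Discharge sample | Discharge |
| Protocol 6.2.4 | Discharge procedures finish at the end of Day 3 | Discharge is after use |
| Protocol 9.5, Table 7 | Not in the rows before T0; appears beside breakfast, up to 2 hours after T0 | Post-use, but weak: cells may be merged |
| SAP 8.9 | At discharge | Discharge |
| SAP 12.3, CLBD and shift shell | Baseline and Discharge; shift shell headed as post-use | Discharge |

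SAP 8.10 is informative by contrast. It lists vital signs before use in each of the three periods and also at discharge in Period 3. The SAP therefore treats pre-use and discharge on Day 3 as separate time points, and SAP 8.9 gives the laboratory panel only the second.

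**3. What does the rule do if the draw is post-use?** Take the six sequences of P1R, P1M and CIG. The protocol names the Day 2 product. SAP 8.8 names the most recently used product, which after Day 3 use is the Day 3 product. (Its washout sentence speaks of the time between products; I extend the same principle to the interval from Day 3 use to discharge.)

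| Day 1 – Day 2 – Day 3 | Protocol 12.5.2 | SAP 8.8 | Crosses THS/CIG? |
|---|---|---|---|
| P1R – P1M – CIG | P1M | CIG | Yes |
| P1R – CIG – P1M | CIG | P1M | Yes |
| P1M – P1R – CIG | P1R | CIG | Yes |
| P1M – CIG – P1R | CIG | P1R | Yes |
| CIG – P1R – P1M | P1R | P1M | No |
| CIG – P1M – P1R | P1M | P1R | No |

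The rules differ in 6 of 6 sequences. In 4 of 6 the label crosses between THS and cigarette, and in 2 of 6 it swaps the two sticks. The result is the same whether the post-use draw is soon after T0, as Table 7 might suggest, or at discharge.

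**4. And if the draw is pre-use?** The last product used before the draw is the Day 2 product. With a known onset time both rules name it, so they differ in 0 of 6 sequences.

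**5. What can one draw show?** A pre-use Day 3 draw follows two products and a post-use draw follows three. Neither isolates one product.

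**The case against.** The best defence is that silence is not contradiction. SAP 8.8 does not revoke the protocol rule, and SAP 9 says the documents agree, so the rule could be read as still in force. On the protocol's own premise the two rules coincide. This stands for a pre-use draw. It does not help if the sample is taken at discharge, because the SAP then states both a draw time that removes the premise and a general rule that gives a different answer.

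Discharge might be only a visit label. SAP 8.10 weighs against that, since it separates pre-use from discharge on the same day.

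Some of the timing evidence is weak, and this should be conceded. Permission for a non-fasting sample says nothing about T0. Table 7 may have merged cells, protocol 9 allows a procedure without a start time to be done at any hour, and SAP 12 says shells may change. The finding rests on SAP 8.9 and protocol 7.5.1, with the shells in support.

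A real safeguard exists. The AE listing shell (Appendix 16.2.7.1) shows product, time from last use and start time for each AE, and protocol 8.2.4 requires a causality assessment. A reader could re-attribute events one by one. That does not correct the by-product tables.

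Two stronger readings are tempting. One is that a single Day 3 laboratory AE could land under the Day 2 product, the Day 3 product, both, or the safety follow-up column. The last two need a missing onset time, or an onset taken from the result date after discharge. No passage prescribes either, so these are data-dependent branches and not competing instructions. The other is a count of mislabelled subjects. That would need a laboratory AE rate, which the documents do not give, and equal allocation across sequences, whose details sit in a separate randomization plan.

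**Conclusion.** The point holds in a conditional form and should be corrected. The attribution rule in protocol 12.5.2 rests on a draw time that its cited source does not contain and that protocol 7.5.1, SAP 8.9 and the laboratory shells contradict. If the draw is at discharge, the rule names a different product from SAP 8.8 in 6 of 6 sequences, crossing THS and cigarette in 4 of 6, and the alignment statement in SAP 9 is then wrong on this point. If the draw is pre-use with a known onset time, nothing changes.

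These are counts of sequences, not of subjects or events. Reporting an abnormal finding as an AE is at the investigator's discretion (protocol 8.4), so the number of affected events may be small or zero. A different label is also not the same as a wrong one, since no single Day 3 draw can identify the responsible product. The effect is confined to by-product tabulation of laboratory AEs. PK and the main objective are untouched. The conclusion assumes that no text of 12.5.2 beyond what was available for review qualifies the rule.

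**What to change.** - Reconcile protocol 12.5.2, 7.5.1, Table 7 and Appendix A with SAP 8.9 on when the Day 3 safety samples are taken relative to T0, and state it once.
- Replace the fixed previous-day rule with one rule worded identically in protocol 12.5.2 and SAP 8.8: a laboratory-detected AE is attributed to the last product used before the recorded draw time. This is a convention, since a change may precede the draw that detects it, but it gives a single answer whichever draw time is confirmed.
- State beside the rule that the Day 3 draw follows two products (pre-use) or three (post-use) and cannot isolate one.
- List any remaining difference between protocol and SAP in SAP 9.

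The cost is a few sentences in each document. No new data are needed, because the laboratory listing shell (Appendix 16.2.8.1) already carries date and time.

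Shells CLBD, CVS, CEG and CSP show sequence columns only, although protocol 12.1.2 also asks for safety summaries by product and overall. That is a separate, minor point and should be handled on its own.
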